11	STUDY MONITORING AND AUDITING	56
12	RETENTION OF RECORDS	57
13	DISCLOSURE OF DATA.....	57
14	REFERENCES.....	57

LIST OF TABLES

Table 1: Schedule of Events.....	16
Table 2: Dermal Response Scale (Draize)	44
Table 3: Erythema of the Study Chalazion	45

LIST OF ABBREVIATIONS AND DEFINITIONS OF TERMS

Abbreviation	Definition
ADL	Activities of Daily Living
AE	Adverse Event
CFR	Code of Federal Regulation
CR	Complete Response
CRA	Clinical Research Associate
CRF	Case Report Form
CTCAE	Common Terminology Criteria for Adverse Events
EC	Ethics Committee
eCRF	Electronic Case Report Form
EDC	Electronic Data Capture
eDCF	Electronic Data Clarification Form
FDA	Food and Drug Administration
GCP	Good Clinical Practice
GLP	Good Laboratory Practice
ICF	Informed Consent Form
ICH	International Council for Harmonisation
IOP	Intraocular Pressure
IP	Investigational Product
IRB	Institutional Review Board
ITT	Intent-to-Treat
IUD	Intrauterine Device
IWRS	Interactive Web-Based Response System
LC/MS-MS	Liquid Chromatography-Mass Spectrometry
LLOQ	Lower Limit of Quantification
MAD	Multiple Ascending Dose
MKP-1	Mitogen-Activated Protein Kinase Phosphatase-1
MedDRA	Medical Dictionary for Regulatory Activities
mITT	Modified Intent-to-Treat
NCI	National Cancer Institute
PI	Principal Investigator

Abbreviation	Definition
PP	Per-Protocol
PRO	Patient Reported Outcome
REB	Research Ethics Board
SAD	Single Application Dose
SAE	Serious Adverse Event
SoC	Standard of Care
SOC	System Organ Class
TDS	Transdermal System
TEAE	Treatment Emergent Adverse Event
US	United States
VA	Visual Acuity
VAS	Visual Analog Scale
WHO	World Health Organization

INVESTIGATOR STATEMENT

I have read and understand the protocol and agree to implement the study in accordance with the procedures set forth in the protocol and in accordance with the sponsor's guidelines, all applicable government regulations, and the International Council for Harmonisation Good Clinical Practice Guidelines E6 (ICH GCP).

I will maintain accurate source documents from which data are entered onto electronic case report forms and accurate drug accountability records that show the receipt and disposition of all study drugs.

I will provide adequate protocol training to my associates, colleagues, and employees assisting in the conduct of the study.

I will obtain Institutional Review Board/Ethics Committee (IRB/EC) approval of the protocol and Informed Consent Form (ICF) prior to enrollment of subjects in the study. I understand that any modifications to the protocol made during the course of the study must first be approved by the IRB/EC prior to implementation except when such modification is made to remove an immediate hazard to the subject.

I will ensure that a fully executed IRB approved ICF is obtained from each subject prior to initiation of any study procedures.

I will report (within 24 hours) any serious adverse event (SAE), regardless of relationship to study drug, or pregnancy that occurs during the course of the study, in accordance with the procedures described in Section 6 of the protocol. I will notify the sponsor if I become aware that a partner of a study subject becomes pregnant while the subject was receiving this study drug.

I will submit all protocol inclusion/exclusion violations to the medical monitor for approval prior to enrollment of the subject in the study.

I will allow the sponsor, Senju USA, Inc. and its agents, as well as the United States (US) Food and Drug Administration (FDA) and other regulatory agencies to inspect study facilities and pertinent records at reasonable times and in a reasonable manner, ensuring subject confidentiality. If I am notified that this study is to be inspected by a regulatory agency, I will notify the sponsor as soon as possible thereafter (no later than 1 week).

This protocol contains information that is proprietary to Senju USA, Inc. The information contained herein is provided for the purpose of conducting a clinical trial for Senju USA, Inc.

The contents of this protocol may be disclosed to study personnel under your supervision and to your IRB/EC. The contents of this protocol may not be disclosed to any other parties (unless such disclosure is required by government regulations or laws) without the prior written approval of Senju USA, Inc.

Investigator's Signature

Date

SYNOPSIS

Study Title (Protocol Number)	A Multi-Center, Double-Masked, Randomized, Placebo-Controlled Evaluation of the Safety and Efficacy of SUN-131 Transdermal System (TDS) as Compared to Placebo TDS in Patients with a Chalazion (SUN-131-03)
Phase	Phase 3
Study Drug	SUN-131 1.5% TDS
Objectives	To evaluate the efficacy and safety of SUN-131 1.5% TDS as compared with placebo TDS in the treatment of chalazion
Study Design	
This is a prospective multi-center, double-masked, randomized, placebo-controlled clinical trial. Subjects will be centrally randomly assigned in a 1:1 ratio to receive one of the following treatments in the affected eyelid:
 
SUN-131 1.5% TDS (n = 130) Placebo TDS (n = 130)
 
The randomization will be stratified by age group (<12 years, ≥12 years). All study drug will be worn for a minimum of 16 hours and a maximum of 24 hours each day for 14 days.
 
The following items will be assessed at screening/baseline and at 30 minutes to 1 hour after patch removal on Days 8 ± 1 and 15 ± 1.
 
 • Presence of a chalazion by examination (clinical assessment) • [REDACTED] • Erythema of the chalazion site itself as measured by a 5-point scale (0 = no sign of erythema, 1 = slight erythema, 2 = mild erythema, 3 = moderate erythema, 4 = severe erythema) • Pain in study eyelid and eye of the study eyelid related to chalazion as measured by Visual Analog Scale (VAS) of 100 mm 
Patient Reported Outcome (PRO) will be assessed by a self-evaluation diary of chalazion (present or absent), completed daily by the subjects from Day 1 through Day 15 ± 1.

Sample Size	Approximately 260 subjects will be randomized.
Study Population	Male or female subjects aged ≥ 6 years with a chalazion
Inclusion Criteria	
Subjects eligible to participate in the study must meet all of the following criteria:
 
 1. Subjects aged ≥ 6 years of either sex and of any race. 2. Subjects with a diagnosis of a single chalazion with visible granuloma in the study eyelid. Study eyelid may be either an upper or lower eyelid. 3. Subjects with a chalazion with the granuloma area (height x width) ≤ 36 mm² when measured by a caliper. 4. Subjects with chalazion erythema score of ≥ 1 (as graded on a 5-point scale: 0 = no erythema, 1 = slight erythema, 2 = mild erythema, 3 = moderate erythema, 4 = severe erythema). 5. Chalazion intended for study treatment present for no more than 21 days based on patient history on Day 1. 6. Normal eyelid function without active signs of eye/eyelid infection in either eye.

[figure not shown]
	
 7. Must be willing and able to correctly apply and wear a transdermal patch to the eyelid for minimum of 16 hours and a maximum of 24 hours each day for the entire study treatment period, or have someone (guardian/caregiver) in the household who is willing and able to correctly apply a transdermal patch for the subject. 8. Female subjects must be 1-year postmenopausal, surgically sterilized or, if of childbearing potential, must have a negative urine pregnancy test on Day 1, and must agree to use a method of contraception for the entire study period. Approved methods of contraception include: abstinence, oral contraceptives, an intrauterine device (IUD) with spermicide, a female condom with spermicide, a diaphragm with spermicide, a cervical cap with spermicide, use of a condom with spermicide by sexual partner or a sterile sexual partner. 9. If male, subjects must be sterile or willing to use an approved method of contraception for the entire study period. Males must be willing to refrain from sperm donation for the entire study period. 10. Are able and willing to attend all study visits and follow all study-related instructions. 11. Have signed written informed consent before undergoing any study-related procedures and is willing to comply with all study procedures; or signed written consent from parent or legal guardian if the subject is a minor and signed written assent from subject, if appropriate. 12. Avoid wearing contact lenses in the study eye or using any new facial cosmetic products during the study period. 13. Avoid wearing any make-up, ointment, or moisturizer on the study eyelid where the study drug is applied (mascara on the eyelash is allowed) during the entire study period. 14. Ability to reliably report symptoms.

Exclusion Criteria
	
Subjects who meet the following criteria are not eligible to participate in this study:
 
 1. Chalazion that has atypical features (a recurring chalazion at the same spot, abnormal surrounding lid tissue, associated loss of tissues). 2. History of chalazion incision and curettage in study eyelid. 3. Chalazion at the eyelid margin (≤ 2 mm distant from the edge of the study eyelid margin). 4. Multiple chalazia in the study eyelid or in any non-study eyelid(s). A single chalazion in any non-study eyelid(s) is(are) allowed. 5. Chalazion on the eyelid that was previously screen failed. Re-screening of the same subject is allowed only once. 6. Chalazion on the same eyelid or the opposing eyelid (i.e. same side) of the eyelid which was previously enrolled. Re-entry of the same subject is allowed only once. 7. Active ocular or eyelid infection (bacterial, viral, or fungal), or condition in the study eye/eyelid that in the investigator's opinion could affect the subject's health or the study parameters. 8. Presence of hordeolum in any one eyelid. 9. An abnormal skin condition on the study eyelid region (e.g., eczema, psoriasis, atopic dermatitis, etc.) where the study drug will be applied. 10. Intraocular pressure (IOP) greater than 22 mmHg in either eye. 11. Diagnosed with glaucoma in either eye. 12. History of steroid-induced elevation of IOP.

[figure not shown]
	
13. Use of systemic (intravenous, intramuscular, oral), ophthalmic, or dermatological corticosteroids or immunosuppressant within 4 weeks prior to Day 1 and throughout the study period. Inhalant, intranasal, intra-articular, and perianal steroids are permitted.
 
14. Use of systemic or ophthalmic azithromycin in either eye within 5 weeks prior to Day 1 and throughout the study period, use of other systemic or ophthalmic macrolides (e.g. erythromycin, clarithromycin, etc.) in either eye within 2 weeks prior to Day 1 and throughout the study period, and use of tetracyclines (e.g. tetracycline, doxycycline, etc.) in either eye within 2 weeks prior to Day 1 and throughout the study period.
 
15. Use of periocular or intraocular corticosteroid injection or corticosteroid depot in either eye within 9 weeks prior to Day 1 and throughout the study period.
 
16. Female subjects who are pregnant or lactating.
 
17. Known allergy or sensitization to the test article or any formulation components.
 
18. History or evidence of ocular surgery in either eye or eyelid within the past 3 months.
 
19. History of refractive surgery in either eye within the past 6 months.
 
20. Planned surgery (ocular in either eye or eyelid or systemic) during the entire study period.
 
21. Participation in an investigational study within 30 days prior to Day 1.
 
22. Have any ocular condition in either eye that requires chronic use of topical ophthalmic medication (e.g., glaucoma, dry eye, allergic conjunctivitis) with exception of over-the-counter artificial tears or lubricant eye drops, anti-histamine drops, or that, in the investigator's opinion, supports the safe use of the study drug.
 
23. History of any previous functional or cosmetic eyelid surgery (including blepharopigmentation) in the study eyelid.
 
24. Any other condition that, in the opinion of the investigator, renders the subject unsuitable for study participation.


Dosage and Administration of Study Drug
	
This study will consist of up to 3 visits and one telephone contact occurring over a maximum 25-day period. Subjects (or the caregiver) will apply the study drug on the study eyelid daily in the clinic or at home after completing training at the site. Subjects will keep the study drug on the eyelid for a minimum of 16 hours and a maximum of 24 hours each day for 14 days. Gently cleanse the study eyelid and allow it to dry for approximately 30 minutes before applying a new study drug. On Days 8 ± 1 and 15 ± 1, the study drug should not be replaced with to a new study drug in the morning of the visit to ensure the study drug is worn for a minimum of 12 hours before removal by the investigator at the site. The subject may wear the study drug over 24 hours on these visit days if necessary. On Day 8 ± 1, subjects should apply a new study drug after completion of evaluations to ensure the study drug is worn for minimum of 16 hours on that day. The subject can then return to their normal schedule of study drug removal and replacement. Subjects will document time/date of each application and removal in the diary as well as any unusual events.

Efficacy Measures
	
The following items will be assessed at screening/baseline (Day 1), at 30 minutes to 1 hour after patch removal on Days 8 ± 1, and 15 ± 1.
 
 • Presence of a chalazion by examination (clinical assessment) • [REDACTED]

	
 Erythema of the chalazion site itself as measured by the 5-point scale Pain in study eyelid and the eye of the study eyelid related to chalazion as measured by VAS of 100 mm 
PRO will be assessed by self-evaluation diary of chalazion (present or absent), completed daily by the subjects from Day 1 through Day 15 ± 1.
 
Primary Outcome Measure: Signs (Objective)
 
 Complete Response (CR) of the study chalazion by Day 15 ± 1. 
Complete response is defined as the absence of any significant clinical signs of a chalazion, based on clinical judgment by an investigator. Scarring or skin defects resulting from healing of the chalazion are possible and allowed upon CR.
 
[REDACTED]
 
Additional Secondary Outcome Measures: Signs (Objective)
 
 Change in size of the study chalazion from baseline to Days 8 ± 1 and 15 ± 1. Change in erythema of the study chalazion from baseline to Days 8 ± 1 and 15 ± 1. 
Symptoms (Subjective)
 
 Change in pain associated with the study chalazion in the study eye and eyelid assessed in VAS from baseline to Days 8 ± 1 and 15 ± 1.
Safety Measures	
Adverse events (AEs) (observed or reported verbally or via diary) will be obtained following the first study drug application on Day 1 through Day 22 ± 3.
 
The following assessments will be done in both eyes at baseline (pre-dose on Day 1), and after patch removal on Days 8 ± 1 and 15 ± 1.
 
 Visual acuity (Snellen charts) Slit-lamp biomicroscopy (lid, conjunctiva, cornea, anterior chamber and lens) IOP measurement (Goldmann tonometer, Tono-Pen, or iCARE) 
Skin irritation of the TDS application site will be assessed in the study eyelid by the investigator at baseline (pre-dose on Day 1) and 30 minutes to 1 hour after patch removal by the study staff on Days 8 ± 1 and 15 ± 1 by using the 5-point Draize scale (0: No evidence of erythema, 1: Very slight erythema, 2: Well defined erythema, 3: Moderate to severe erythema, 4: Severe erythema [beet redness] to slight eschar formation [injuries in depth]).

Other Measures	
 • Patch adhesion will be assessed by the investigator prior to patch removal on Days 8 ± 1 and 15 ± 1 in the study eyelid only. (0: ≥ 90% adhered, 1: ≥ 75% to < 90% adhered, 2: ≥ 50% to < 75% adhered, 3: < 50% adhered, 4: patch completely off the skin). • Ocular and skin comfort query of the eye of the study eyelid and the study eyelid (comfort from study drug application) as measured in VAS of 100 mm length are to be conducted at baseline (Day 1 prior to study drug application), and prior to patch removal on Days 8 ± 1 and 15 ± 1. • Residual drug content of the used study drug collected at the site on Days 8 ± 1 and 15 ± 1 will be evaluated.
Study Duration	It is planned that each subject will participate in the study for a maximum of 25 days. Overall duration of the study will be approximately 10 months, depending on the rate of enrollment and number of subjects enrolled.
Study Centers	Up to 67 clinical sites

Table 1: Schedule of Events

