The anti-inflammatory and immunosuppressive effects of glucocorticoids, such as [REDACTED], rely on several molecular mechanisms, that have been elucidated by basic research (1). Three main mechanisms include direct effects on gene expression by the binding of glucocorticoid receptors to glucocorticoid-responsive elements (i.e., the induction of annexin I and mitogen-activated protein kinase phosphatase 1 [MKP-1]), indirect effects on gene expression through the interactions of glucocorticoid receptors with other transcription factors (i.e., NF- κ B and activator protein 1), and glucocorticoid receptor-mediated effects on second-messenger cascades (i.e., the PI3K–Akt–eNOS pathway). Unfortunately, because some of these mechanisms are also involved in systemic physiologic signaling rather than inflammatory signaling, the therapeutic effects of systemic glucocorticoids in inflammation are often accompanied by clinically significant side effects when given in the systemic circulation. Given that the target indication is a chalazion, targeting the application of [REDACTED] to the site of inflammation is considered the most effective approach with the least potential for systemic or ocular side effects.

The SUN-131 ([REDACTED]) TDS is designed for local delivery of a corticosteroid, [REDACTED], to the upper or lower eyelid. This TDS is specially engineered to gently adhere to the eyelid and is shaped to fit the contours of the eye. The backing and adhesives used are also designed to allow removal of the patch without causing irritation and to be flexible for adequate comfort. Thus, targeted local delivery of [REDACTED] to treat the chalazion can be achieved from this unique transdermal design without significant exposure of the active agent to the eye, as with ointment or drops. Thus, this is considered a dermal application of a

TDS to treat a local extra-ocular disease in the eyelid. The low local dose also will minimize any potential for systemic exposure and minimize exposure to the eye.

[Redacted text block]

[Redacted text block]

[Redacted text block]

[Redacted text block]

1.1 Phase 1 Clinical Evaluation of the SUN-131 TDS:

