Subjects meeting all inclusion criteria and none of the exclusion criteria will be enrolled into the study. Training will be conducted on study procedures and on the appropriate method to apply and remove the study drug. Subjects will be centrally randomly assigned in a 1:1 ratio to receive SUN-131 1.5% TDS or placebo TDS applied to the study eyelid affected by the chalazion. The randomization will be stratified by age group (<12 years, ≥12 years). Subjects will receive a 1-week supply of study drug, including backup study drug, and be instructed to wear the study drug daily for a minimum of 16 hours and a maximum of 24 hours, and gently cleanse and wipe the study eyelid and to allow it to dry for approximately 30 minutes before applying a new study drug.

Subjects will continue to apply the study drug each day on the study eyelid for the full treatment period. Subjects will record the time of study drug application, study drug removal, and any unusual events or patch adhesion issues in a daily subject diary, as well as any missed/fall-off/misapplications. Subjects will keep all used and unused study drug in a provided container and return to the sites.

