4.1.1 Inclusion Criteria

Subjects eligible to participate in the study must meet all of the following criteria:

1. Subjects aged ≥ 6 years of either sex and of any race
2. Subjects with a diagnosis of a single chalazion with visible granuloma in the study eyelid. Study eyelid may be either an upper or lower eyelid.
3. Subjects with a chalazion with the granuloma area (height x width) $\leq 36 \text{ mm}^2$ when measured by a caliper.
4. Subjects with chalazion erythema score of ≥ 1 (as graded on a 5-point scale: 0 = no signs of erythema, 1 = slight erythema, 2 = mild erythema, 3 = moderate erythema, 4 = severe erythema).
5. Chalazion intended for study treatment present for no more than 21 days based on patient history on Day 1.
6. Normal eyelid function without active signs of eye and eyelid infection in either eye.
7. Must be willing and able to correctly apply and wear a transdermal patch to the eyelid for minimum of 16 hours and maximum of 24 hours each day for the entire study treatment period, or have someone (guardian/caregiver) in the household who is willing and able to correctly apply the transdermal patch for the subject.
8. Female subjects must be 1-year postmenopausal, surgically sterilized, or women of childbearing potential must have a negative urine pregnancy test on Day 1, and must agree to use a method of contraception for the entire study period. Approved methods of contraception include: abstinence, oral contraceptives, an IUD with spermicide, a female condom with spermicide, a diaphragm with spermicide, a cervical cap with spermicide, use of a condom with spermicide by sexual partner, or a sterile sexual partner.
9. If male, subjects must be sterile or willing to use an approved method of contraception for the entire study period. Males must be willing to refrain from sperm donation for the entire study period.
10. Are able and willing to attend all study visits and follow all study-related instructions.
11. Have signed written informed consent before undergoing any study-related procedures and is willing to comply with all study procedures; or signed written consent from parent or legal guardian if the subject is a minor and signed written assent from subject, if appropriate.
12. Avoid wearing contact lenses in the study eye or using any new facial cosmetic products during the study period.

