4.1.2 Exclusion Criteria

Subjects who meet the following criteria are not eligible to participate in this study:

1. Chalazion that has atypical features (a recurring chalazion at the same spot, abnormal surrounding lid tissue, associated loss of tissues).
2. History of chalazion incision and curettage in study eyelid.
3. Chalazion at the eyelid margin (≤ 2 mm distant from the edge of the study eyelid margin).
4. Multiple chalazia in the study eyelid or in any non-study eyelid(s). A single chalazion in any non-study eyelid(s) is(are) allowed. .
5. Chalazion on an eyelid that was previously screen failed. Re-screening of the same subject is allowed only once.
6. Chalazion on the opposing eyelid (i.e. same side) of an eyelid which was previously enrolled. Re-entry of the same subject is allowed only once.
7. Active ocular or eyelid infection (bacterial, viral, or fungal), any ocular or eyelid condition in the study eyelid/eye of study eyelid that in the investigator's opinion could affect the subject's health or the study parameters.
8. Presence of hordeolum in any one eyelid.
9. An abnormal skin condition on the study eyelid region (e.g., eczema, psoriasis, atopic dermatitis, etc.) where the study drug will be applied.
10. Intraocular pressure greater than 22 mmHg in either eye.
11. Diagnosed with glaucoma in either eye.
12. History of steroid-induced elevation of IOP.
13. Use of systemic (intravenous, intramuscular, oral), ophthalmic, or dermatological corticosteroids or immunosuppressant within 4 weeks prior to Day 1 and throughout the study period. Inhalant, intranasal intra-articular, and perianal steroids are permitted.
14. Use of systemic or ophthalmic azithromycin in either eye within 5 weeks prior to Day 1 and throughout the study period, use of other systemic or ophthalmic macrolides (e.g. erythromycin, clarithromycin, etc.) in either eye within 2 weeks prior to Day 1 and

throughout the study period, and use of tetracyclines (e.g. tetracyclines, doxycyclines, etc.) in either eye within 2 weeks prior to Day 1 and throughout the study period.

15. Use of periocular or intraocular corticosteroid injection or corticosteroid depot in either eye within 9 weeks prior to Day 1 and throughout the study period.
16. Female subjects who are pregnant or lactating.
17. Known allergy or sensitization to the test article or any formulation components.
18. History or evidence of ocular surgery in either eye or eyelid within the past 3 months.

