4.4 Method of Randomization and Treatment Assignment

Each subject who is entered into the study will be assigned a screening number. The screening number will consist of the 2-digit site number (##) and a 3-digit sequential number (XXX). The subject screening number (##-XXX) becomes the subject identifier.

For subjects who meet the criteria for randomization, a treatment group randomization code will be assigned to that subject number via an Interactive Web Response System (IWRS). Subjects will then be centrally randomized in a 1:1 ratio to either SUN-131 1.5% TDS or placebo TDS. The randomization will be stratified by age group (<12 years, ≥12 years).

Re-screening of the same subject that has previously screen failed is allowed only once. Re-entry of the same subject that was previously randomized is allowed only once. A new subject number will be issued when the same subject is re-screened or re-enrolled for the study.

The study drug kit will be coded with a three-digit (YYY) kit number. After randomization on Day 1, the IWRS will assign a study drug kit to a subject. On Day 1, the subject will receive a 1-week supply of study drug including backup study drug. On Day 8 ± 1, the subject will visit the site, return all used and unused study drug, and be provided with another 1-week supply of study drug including backup study drug. On Day 15 ± 1, the subject will visit the site and return used and unused study drug.

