7.1.1 Analytical Populations

- **Intent-to-Treat:** The ITT population will include all randomized subjects. All primary and secondary efficacy analyses are to be on the ITT population.
- **Modified Intent-to-Treat:** The mITT population will include all randomized subjects with at least one post-baseline primary outcome assessment. Results of the efficacy analyses based on the mITT population will be presented as a sensitivity analysis. Treatment assignments in the mITT population will be based on the treatment to which the subject was randomized.
- **Safety:** The safety population will include all randomized subjects who received the study drug. Treatment assignments in the safety population will be based on the treatment that was received (if different from the randomized treatment).
- **Per-Protocol:** The PP population will exclude from mITT population those subjects who have major protocol violations. Major protocol violations include violation of entry criteria, receiving the incorrect randomization, noncompliance with study drug administration (missing the study drug administration more than 80% of study drug or failure to apply the study drug for at least 5 days per week and miss more than 2 of 7 days of application), and the use of prohibited medications. Treatment assignments in the PP population will be based on the treatment that was received (if different from the randomized treatment).

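### The Investigator Statement opens a route for approving known eligibility violations before enrolment, which contradicts the protocol's own rule that every criterion must be satisfied

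*Combined protocol and SAP*

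**What the plan says.** The Investigator Statement, signed by each investigator, contains this commitment: "I will submit all protocol inclusion/exclusion violations to the medical monitor for approval prior to enrollment of the subject in the study". It covers all inclusion and exclusion criteria and sets none apart.

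The protocol body states a different rule in four places:

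- Section 4.1.1 introduces the inclusion list with "Subjects eligible to participate in the study must meet all of the following criteria".
- Section 4.1.2 introduces the exclusion list with "Subjects who meet the following criteria are not eligible to participate in this study".
- Section 3.4.1 states: "Subjects meeting all inclusion criteria and none of the exclusion criteria will be enrolled into the study".
- Section 4.4 states: "For subjects who meet the criteria for randomization, a treatment group randomization code will be assigned to that subject number". The code comes through the IWRS.

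On analysis, Section 7.1.1 puts every randomised subject in the ITT population, which is the primary efficacy set. It forms the PP population by removing major violators from the modified ITT set, and says "Major protocol violations include violation of entry criteria".

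**The concern.** An investigator with a subject who narrowly fails a criterion has two instructions. The body says the subject is not eligible. The signed statement says to put the violation to the medical monitor for approval. If approval can be given, every eligibility limit becomes negotiable case by case.

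Two things are at stake. The first is safety. Section 1 says that the "TDS is designed for local delivery of a corticosteroid", and Section 4.1.2 excludes subjects for whom that class is a recognised concern: "Intraocular pressure greater than 22 mmHg in either eye", diagnosed glaucoma and a history of steroid-induced IOP elevation. It also excludes pregnant or lactating women. The approval sentence reaches all of these. The second is the meaning of the result. The limits on granuloma area (36 mm²), duration (21 days) and minimum erythema score (1) define the condition studied, and exceptions to them change the population that the primary result describes.

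**Working it through.** No arithmetic applies. The check compares the texts and then follows an approved subject through the analysis sets.

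1. *What the sentence does.* The thing submitted is a violation, the action sought is approval, and the time is before enrolment. Together these describe a prospective waiver. A duty to report deviations after the event would use none of the three.

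2. *Whether the body allows it.* It does not. Sections 4.1.1 and 4.1.2 define eligibility without exception, Section 3.4.1 limits enrolment to eligible subjects, and Section 4.4 limits the randomisation code to those who qualify. For a subject who fails, Sections 4.1.2 and 4.4 provide for screen failure and one re-screening. Exclusion 5 bars a chalazion on an eyelid that has already screen failed, so a near miss cannot simply return with the same eyelid. That gives sites some reason to seek approval instead.

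3. *Whether anything limits the route.* No section gives grounds for approval, criteria that may not be waived, documentation, or notice to the IRB/EC. The Investigator Statement itself requires IRB/EC approval before a protocol modification is implemented, except to remove an immediate hazard. It does not say how an approved eligibility violation fits with that.

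4. *What happens to an approved subject in the analysis.* Once randomised, the subject is in ITT by definition and counts in the primary chi-square test (Section 7.1.5.1). The subject has also violated an entry criterion and is therefore excluded from PP. Section 7.1.1 does not separate approved from unapproved violations. Section 4.1.3 also lists a protocol violation among the reasons for which the investigator may withdraw a subject.

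5. *Whether this biases the comparison.* Approval would precede enrolment and randomisation. Allocation is central (Section 4.4), and sites and sponsor are masked (Section 4.4.2). An approval therefore cannot depend on the arm, and the ITT comparison stays a valid randomised one. What can change is the population to which it applies.

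6. *Size.* The documents give no expected number of approvals and no rate from which one could be derived.

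**The case against.** The strongest defence is that this is one sentence in a signature statement and that the operative protocol is already strict. The same statement binds the investigator to the protocol's procedures and to GCP. No operative section describes a waiver step, and Section 4.4 already ties randomisation to meeting the criteria. The sentence could be meant only as a gatekeeping or notification step, and the medical monitor may refuse every request. It stands that the sentence creates a possibility and nothing more. The gatekeeping reading, however, fits the words poorly and no other section confirms it. If it is what was meant, the sentence misstates it and still needs correcting.

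A reader might infer more than the documents support:

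- *That violators will be enrolled, or that the trial plans to randomise subjects it regards as unevaluable.* The text asks for approval and does not say that approval is given.
- *That the ITT population would no longer be the one defined.* Section 7.1.1 defines ITT as everyone randomised, so an approved subject belongs in it. The departure would be from the eligibility criteria.
- *That violations would be hidden.* Section 7.1.2 provides a list of subjects with protocol violations and what each one was.
- *That nobody oversees safety.* Section 3.1 rules out monitoring committees but has the medical monitor review data and safety periodically. Ocular safety, including IOP, is examined in both eyes at baseline and around Days 8 and 15 (Sections 3.5.4 and 5.2). It remains true that the same role would approve exceptions and review safety.
- *That pregnant women are likely to be admitted.* Section 6 requires treatment to stop once a pregnancy is reported, so a knowing approval would contradict a further passage. The approval sentence still does not exempt this exclusion.

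**Conclusion.** The contradiction is real and rests on the text alone. The Investigator Statement makes known eligibility violations approvable before enrolment with no criterion exempted, while Sections 3.4.1, 4.1.1, 4.1.2 and 4.4 admit no exceptions. It should be corrected.

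The consequences are conditional on approvals being granted. In that case the enrolled population could depart from the stated criteria, subjects whom the protocol names as ineligible could be exposed to the study drug, and ITT and PP would differ by those subjects. The randomised comparison would not be biased. Any percentage of the planned 260 subjects put forward as a waiver rate would be a guess, and the point does not depend on one. The conclusion assumes that the sentence means what it says and that no document outside the protocol restricts it.

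**What to change.** Reconcile the Investigator Statement with Sections 3.4.1, 4.1 and 4.4. Replace the sentence with one that applies the rule already in the body and says three things: the investigator will not enrol a subject who fails an inclusion criterion or meets an exclusion criterion; no prospective eligibility waivers will be granted; and an eligibility deviation discovered after enrolment will be reported to the medical monitor and recorded as a protocol deviation. No criterion needs to change.

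In Section 4.4, state that the IWRS assigns a randomisation code only after the site has confirmed that all criteria are satisfied. Section 4.4 already implies the condition; the explicit confirmation is what is new.

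The cost is one sentence and one IWRS confirmation field. The small downside is losing the few subjects who might otherwise have been approved.
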